1. STUDY OVERVIEW

1.1. Significance of Breast Cancer Diagnosis

Breast cancer is a heterogeneous disease with different histologic subtypes composed of different grades, growth rates, and metabolic activity levels resulting in a wide range of functional differences (1). Additionally, benign breast disease encompasses a heterogeneous group of lesions that vary in vascular content, proliferative index, and metabolic activity, all of which may or may not be associated with future risk of breast cancer (2). X-ray mammography is routinely used for breast cancer screening and diagnosis. Ultrasound (US) of the breast is frequently used as a complement to mammography and breast MRI (3), and may aid in screening dense breasts (4-5). Contrast enhanced mammography (CEM) is an FDA approved emerging technology indicated for lesion evaluation, determination of malignancy extent, neoadjuvant treatment response and as a substitute to MRI for high risk screening (6-9). While the characteristics of malignant and benign breast lesions are well established by conventional imaging techniques (10-12), the overlapping appearances of malignant and benign abnormalities result in hundreds of thousands of unnecessary biopsies, i.e. biopsies yielding benign results. (13) The positive predictive value of a screen detected abnormality recommended for biopsy is just over 25%, resulting in nearly 75% of unnecessary biopsy recommendations (14). An optical tomography system that adds functional information like tumor related hemoglobin concentration may improve the accuracy of the breast US exam. In particular, total Hemoglobin (tHb) values falling below a minimum value in the setting of a low or moderate suspicion abnormality (Breast Imaging and Database System, BI-RADS 4A or 4B assessment) may allow the diagnostic radiologist to downgrade the assessment to probably benign or benign (BI-RADS 3 or 2) and thereby reduce the rate of benign biopsies. In a previous study when a minimum threshold value of $tHb < 50\mu m$ was used 45% of BI-RADS 4A and 4B abnormalities that subsequently were proven to be benign could have safely avoided biopsy [34]. At this point in time we have accrued and preliminarily analyzed results from 35 patients (In addition to the initial 20 patients, 15 patients from phase 2 were also analyzed). When using $tHb < 50\mu m$ as a minimum threshold 12 patients with BI-RADS 4A or 4B abnormalities could be downgraded to a probably benign assessment and could have avoided biopsy, suggesting a 35% (12/35) reduction in benign biopsies.

Furthermore, there is an additional clinical scenario that US-guided DOT may have a beneficial impact, in cases with discordant imaging pathology correlation in the setting of a high suspicion US abnormality. In current practice, if a high suspicion (BI-RADS 4C) lesion has a benign pathology result, it may be considered to have discordant imaging pathology correlation and is frequently recommended for repeat biopsy or surgical excision (15). However, if the optical exam shows subthreshold tHb concentration, this may allow for less aggressive management, such as short term follow-up rather than additional tissue sampling. This is particularly applicable to a high suspicion irregular hypo-echoic mass, (which mimics malignancy on standard of care (SOC) US), with biopsy pathology of focal fibrosis. Focal fibrosis typically has low tHb (35).

1.2 **Optical Tomography Using Near Infrared Light Guided or Assisted With Ultrasound (NIR/US)**

Diffuse optical tomography (DOT) and spectroscopy (DOS) have been explored for diagnosis of breast cancer and for predicting and monitoring neoadjuvant therapy responses of advanced or aggressive breast cancer (17-25, 34). Utilizing DOT or DOS alone to perform breast cancer

diagnosis has been reported in many studies using different systems and optical wavelengths in the near infrared spectrum (17-25,34). However, due to intensive light scattering in tissue, lesion localization and light quantification accuracy may not be fully realized (21-22). New approaches taken by researchers in the field include ultrasound guided DOT (24-26, 28, 34), MRI-guided DOT or DOS (29-31), and x-ray guided DOT (32-33). These approaches utilize a conventional imaging modality to guide the DOT or DOS for lesion localization and image reconstruction in order to improve the light quantification accuracy for more accurate diagnosis.

Ultrasound-guided DOT, pioneered by our group, has demonstrated its potential role in differentiating malignant and benign breast abnormalities (24-25, 34), and in predicting and monitoring the neoadjuvant chemotherapy (NAC) response of breast cancer (26). Our unique approach employs a commercial US transducer and NIR optical imaging sensors mounted on a hand-held US probe. The co-registered US is used for lesion localization, and optical sensors are used for imaging tumor related vascularity.

2 OBJECTIVES

We have received 5-year NCI funding to support this study.

The primary objective of this study is to assess the ability of US-guided DOT to reduce the rate of benign biopsy. To achieve this objective we will simultaneously acquire co-registered US imaging data and US-guided DOT imaging data from a group of patients (~300) scheduled for US-guided breast biopsy. We hypothesize that the additional optical information of tHb concentration and distribution will lead to a downgrading of the assessment of a subset of low to moderate suspicion

abnormalities based on conventional imaging (i.e. breast ultrasound with or without mammography) and thereby could lead to a reduction in benign breast biopsies (i.e. false positives).

The secondary and complementary objective is to assess the impact on sensitivity of adjunctive optical data. In particular we hypothesize that by defining a conservative tHb threshold below which malignancy is so rare that the addition of US-guided DOT will not significantly alter the sensitivity of the combined US-guided DOT & CI assessment, i.e. adjunctive US-guided DOT will not decrease true positives.

A third objective is to assess the impact of adjunctive US-guided DOT data in the management of discordant pathology results. In current SOC, the radiologist performing the needle biopsy routinely compares the imaging with the pathology results for concordance. Highly suspicious abnormalities (BI-RAD 4C, 5) that yield benign results are typically considered discordant and are recommended for repeat biopsy or surgical excision. If the discordant abnormality has a tHb below the minimum threshold value, this might allow radiologists to forego a repeat biopsy or surgery. For example, focal fibrosis may appear highly suspicious on US. Our initial data show that fibrotic lesions have low vascularity (28).

Additionally as an exploratory objective, we will compare the results of US-guided DOT and in particular tHb concentration with contrast enhanced mammography (CEM) in the subset of patients who undergo CEM.

3 ELIGIBILITY CRITERIA

Inclusion Criteria:

- Female subjects \geq 18 years old with ultrasound visible breast abnormalities (BI-RADS 3*, 4A, 4B, 4C, and 5) referred for ultrasound-guided core needle biopsy or fine needle aspiration
- Willing and able to provide informed consent

(*note that while a BI-RADS 3 assessment is probably benign, a subset of patients with this assessment choose to undergo biopsy rather than follow up imaging).

Exclusion Criteria:

- Lesions located in the darkly pigmented nipple-areolar complex area
- Subjects with breast implants
- Abnormality in the mirror image location of the contralateral breast.
- Additional abnormalities in the same region of the breast that would be included in US-guided DOT imaging of the abnormality undergoing biopsy
- Previous breast irradiation of the mirror image location of the contralateral breast
- Lesions located at previous biopsy sites when biopsy occurred within the last six months.
- Pregnancy
- Superficial abnormalities located entirely within (i.e. less than) 5mm of the overlying skin

3.1 Inclusion of Women and Minorities

Women and members of all races and ethnic groups are eligible for the study.

4. REGISTRATION PROCEDURES

The following steps must be taken in order to register patients to this study:

1. Confirmation of patient eligibility
2. Registration of patient in the Siteman Cancer Center OnCore database
3. Assignment of unique patient number (UPN)

4.1 Confirmation of Patient Eligibility

Confirm patient eligibility by collecting the information listed below:

1. Registering MD's name
2. Patient's race, sex, and DOB
3. Three letters (or two letters and a dash) for the patient's initials
4. Copy of signed consent form
5. Completed eligibility checklist, signed and dated by a member of the study team
6. Copy of appropriate source documentation confirming patient eligibility

4.2 Patient Registration in the Siteman Cancer Center OnCore Database

All patients must be registered through the Siteman Cancer Center OnCore database.

4.3 Assignment of UPN

Each patient will be identified with a unique patient number (UPN) for this study. All data will be recorded with this identification number on the appropriate CRFs.

5 STUDY PROCEDURES

The study will ensue in two phases: phase 1 – training set, and phase 2 prospective trial.

The first 20 patients undergoing US-DOT will comprise the training set to accomplish the aims of:

- 1) assessing US-DOT data,
- 2) assessing intra-observer variability in the assessment of US-DOT data
- 3) assessing inter-observer variability in the assessment of US-DOT data.

For phase 2, the prospective trial, up to 315 patients will be recruited with the expectation that approximately 5% will not successfully complete the study so that 300 patients will have valid US-DOT data for the ensuing reader study.

The study flow chart that integrates US-guided DOT collection into the standard of care (SOC) clinical workflow is shown below (figure 3). SOC clinical workflow includes review of patient information and diagnostic information, such as conventional imaging results with BIRADS

[figure not shown]
assessments. The study coordinator will approach eligible patients prior to biopsy to assess their willingness to participate in the study. Patients that are willing to participate will sign informed consent and undergo US-guided DOT imaging before biopsy. A subset of patients will also undergo CEM.

Breast radiologist coinvestigators will perform (or supervise certified breast US technologists) in all NIR/US studies. As noted above, they will not be blinded to any clinical data. The function of the imaging specialist in US guided DOT imaging is to ensure that the correct anatomic location of the index lesion is imaged.

[figure not shown]
The study radiologist that performs/supervises the US-guided DOT imaging will complete CI and US-guided DOT case report forms (CRFs) blinded to the pathology result of the ensuing biopsy. In the event that the patient also undergoes CEM the study radiologist will complete CI and CEM CRFs blinded to the pathology result of the ensuing biopsy. Details of CRF completion and related reader study are noted in section 7 – Data Collection and Analysis below.

Figure 3. Study work flow

Training Set:

Prospective Trial

6. US and OPTICAL IMAGING

A hand-held hybrid probe, consisting of a commercially available US transducer located in the middle and near-infrared source and detector optical fibers distributed at the periphery (see Figure 1), will be used for scans. For each patient, co-registered digital US images from the commercial ultrasound unit and optical measurements from our NIR optical imaging device are acquired simultaneously at multiple locations including the lesion of interest region and the same region in the mirror-image contralateral breast. The contralateral location is chosen as the reference site. The difference between measurements obtained from the lesion and the reference site is used for optical imaging reconstruction. Optical absorption distributions at four different wavelengths are reconstructed and lesion total hemoglobin concentration (tHb), and oxygenated and deoxygenated hemoglobin concentrations (HbO₂ and Hb) are computed from absorption maps. The total data acquisition time is about 10 minutes once the lesion is identified by US. Following each patient study, the near infrared images will be reconstructed by [name] group.

Safety and Setup for Imaging

The US-guided NIR device has been used safely by [name] group in the past 14 years for ~500 patients [24,25,34]. There is no known risk associated with the use of the device. The light sources are low-power laser diodes with wavelengths in the NIR range and are fiberoptic coupled to the probe. The laser light sources can only be activated by pushing a button on the touch screen laptop when the surface of the probe, i.e., the tips of the fibers, is in contact with the skin.

7. DATA COLLECTION AND ANALYSIS

Study specific data will be collected from subjects after informed consent is obtained. The following data may be collected on the patient questionnaire: demographic information (name, DOB, Age, Race and Hispanic or Non-Hispanic) MRN#, imaging reports (e.g. mammography, US, PET, MRI, etc.), core biopsy pathology reports, surgical pathology reports if available, breast cancer risk information, etc.

In some cases, the pathologist may review existing biopsy specimens with special staining to look for signs of increased blood supply and vessel density. This will not require additional slicing of standard of care biopsy specimens; thus, samples will not be labeled or stored for the research study. The results of these tests will not be placed in the patient medical record. The results of these tests may be given to the investigators to correlate to the results of the NIR/US procedures.

[figure not shown]
[name], specialist in breast pathology, will assess pathological findings.

The goal of this study is to assess the impact of adjunctive US-guided DOT on the accuracy of breast biopsy recommendations for abnormalities undergoing US-guided breast biopsy. In particular to assess the effect of combining US-guided DOT with CI to: 1. reduce the rate of benign breast biopsy, i.e. decrease false positive biopsy recommendations, and 2. to maintain sensitivity, i.e. maintain true positive recommendations.

Additional goals of this study are to assess the role of US-guided DOT in managing discordant biopsy results and assess the correlation of optical imaging parameters with the presence

and intensity of contrast enhancement of the abnormality undergoing biopsy in patients who have undergone CEM.

Figure 4 – Reader Study Design

To accomplish the aims of assessing the impact of adjunctive US-guided DOT on reducing benign biopsy recommendation (i.e. FPs), while maintaining sensitivity (i.e. TPs) we will conduct a reader study of the 300 subject trial. Three of four study radiologists will serve as study readers for each case. (To eliminate potential bias a study radiologist performing the biopsy will not serve as a reader for that case.) As noted above the study radiologist who performs or supervises the US-guided DOT exam will be one of the readers. Two additional study radiologist readers will subsequently and independently review the available pre-existing patient information and CI data, (excluding the US-guided biopsy exam) and complete CI and DOT CRFs blinded to the pathology result of the abnormality that underwent biopsy. The CRFs include a BI-RADS assessment. The reader will first complete the CI CRF blinded to the US-guided DOT result, then after reviewing the optical data (tHB concentration and distribution) the reader will complete the DOT CRF including the impact of US-guided DOT information on the BI-RADS assessment, i.e. no change, decreased or increased.

Similar to the CI plus DOT workflow, for cases that have CEM, a CI CRF will be completed first, followed by a CEM specific CRF including a BI-RADS assessment and the impact of CEM on the BI-RADS assessment will be recorded. As noted above, the study radiologist that supervises the US-guided DOT and CEM exams will serve as one of the study readers. For the subsequent two readers we will alternate which adjunctive modality (i.e. CEM or US-DOT) is reviewed first and separate the subsequent review of the second adjunctive modality by a minimum of 4 weeks to prevent recollection bias).

Figure 4 diagrams the core analysis. Combined CI and US-guided DOT BI-RADS 2 and 3 assessments will be considered test negative, and BI-RADS 4A, 4B, 4C, and 5 assessments will be considered test positive. For negative tests, the biopsy proven malignant group (Gc, see Fig. 1(b)) represents false negative results, and the benign group Gd represents true negatives and reflects the potential reduction in benign biopsy recommendation if US-guided DOT were used as SOC. Ga represent true positives and Gb represent false positives utilizing adjunctive US-guided DOT. A comparison of the Ga groups i.e. CI alone vs. CI & DOT will constitute the assessment of the effect of adjunctive US-guided DOT on sensitivity.

A small minority of patients assessed as BI-RADS 3-Probably Benign and recommended for short term follow up imaging on the basis of CI will elect to undergo biopsy. We will separately track the effect of supplemental US-DOT on this small subset.

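### The first reader's CI form is not timed against the repeat ultrasound in the DOT session, so for that reader a second-look ultrasound effect can be recorded as an effect of the optical data

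*Combined protocol and SAP*

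**What the plan says.** All references are to the combined protocol and SAP.

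- **Who the first reader is.** Section 7 states that "the study radiologist who performs or supervises the US-guided DOT exam will be one of the readers".
- **What the DOT session contains.** Section 6 says that "co-registered digital US images from the commercial ultrasound unit and optical measurements from our NIR optical imaging device are acquired simultaneously", at the lesion and at the mirror-image site. The optical images are reconstructed after the patient study.
- **What the first reader does and knows.** Section 5 gives the imaging specialist's function as "to ensure that the correct anatomic location of the index lesion is imaged". It says of the radiologists who perform or supervise the scans that "they will not be blinded to any clinical data".
- **What the other two readers use.** Section 7: "Two additional study radiologist readers will subsequently and independently review the available pre-existing patient information and CI data, (excluding the US-guided biopsy exam").
- **Ordering of the forms.** Section 7: "The reader will first complete the CI CRF blinded to the US-guided DOT result". The DOT form follows, after review of tHb concentration and distribution, and records whether the BI-RADS assessment stayed the same, fell or rose. For the first reader, Section 5 adds only blinding to pathology: "The study radiologist that performs/supervises the US-guided DOT imaging will complete CI and US-guided DOT case report forms (CRFs) blinded to the pathology result".
- **How the endpoint is counted.** Section 7 treats a combined CI and DOT assessment of BI-RADS 2 or 3 as test negative. It assesses the effect on sensitivity by comparing true positives under CI alone with those under CI and DOT. Aim 1.1 in Section 7.1 fixes standard-of-care specificity at 0% and reads the whole estimated specificity as the improvement due to DOT.

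**The concern.** The trial asks what the optical information adds to conventional imaging. For the first reader, two new things can arrive together: a repeat ultrasound and the tHb data. A lesion that looks more benign on a second look may be downgraded whatever its tHb.

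The only ordering rule is that the CI form precedes the DOT result. Because reconstruction follows the scan, a CI form completed before the scan complies, and so does one completed after it. The recorded DOT impact can therefore mean different things from case to case, and between the first reader and the other two. The plan already guards against a related exposure by barring the radiologist who performs the biopsy from reading that case. The visible text has no matching rule for the ultrasound in the DOT session.

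At stake are the attribution of downgrades (true negatives if the lesion is benign, false negatives if malignant) and the sensitivity comparison, which depends on what the CI form contains. If the times are not recorded, the order cannot be recovered later.

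**Working it through.** **1. The two permitted orders for the first reader**

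| CI form completed | New information between CI and DOT forms | CI-to-DOT change reflects | Where a second-look downgrade shows | Counted in primary specificity? |
|---|---|---|---|---|
| Before the repeat ultrasound | Repeat ultrasound and tHb | Both, mixed | DOT form | Yes |
| After it, before reconstruction | tHb only | Optical data | CI form, carried into the final assessment | Yes |

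The last column is the same in both rows because the endpoint takes the final combined BI-RADS and compares it with 0%. Timing therefore decides whether the recorded change and the sensitivity comparison are clean. It does not decide whether a second-look downgrade enters the primary specificity.

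**2. Reproducing the plan's power figure (Section 10.3)**

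Inputs: 210 benign biopsies, null 30%, assumed specificity 45%, one-sided 2.5% exact binomial test.

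- The smallest r with P(X ≥ r | 210, 0.30) ≤ 0.025 is r = 77. The tail probability is 0.0225; at r = 76 it is 0.0315.
- P(X ≥ 77 | 210, 0.45) = 0.9940, which matches the stated 99.4%.

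The arithmetic is sound, so the point concerns attribution. Success needs 77/210 = 36.7%, which is 14 lesions above the 0.30 × 210 = 63 expected under the null.

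**3. Illustration of size**

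The documents give no second-look downgrade rate. Assume that the optical data alone give exactly 30% specificity and that second looks add d percentage points for the first reader only. The visible text does not say how three reads per case become one count, so two cases bracket the effect:

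- first reader alone decides: p = 0.30 + d
- three readers averaged, treated approximately as one binomial with n = 210: p = 0.30 + d/3

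Chance of passing = P(X ≥ 77 | 210, p).

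| d | First reader alone: p | Chance of passing | Three-reader average: p | Chance of passing |
|---|---|---|---|---|
| 0 | 30.0% | 2.2% | 30.0% | 2.2% |
| 5 points | 35.0% | 33.0% | 31.7% | 7.0% |
| 7 points | 37.0% | 56.6% | 32.3% | 10.3% |

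If instead 5% of the *remaining* 70% of benign lesions are downgraded, then d = 0.05 × 70 = 3.5 points. The chances are 18.4% (p = 33.5%) and 5.1% (p = 31.2%).

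**4. Number of reads**

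300 cases × 3 readers = 900 reads, of which 300 are first-reader reads. That is an upper bound on the reads whose CI-to-DOT change is mixed. It is reached only if every first-reader CI form precedes the scan and the radiologist views the lesion each time.

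**The case against.** The strongest objection is that timing is not what drives the primary result. With the final BI-RADS set against a fixed 0%, moving the CI form to after the scan leaves a second-look downgrade among the true negatives. The same comparator credits DOT with a downgrade that any of the three readers makes on CI alone. This stands. A reader might infer that locking the form cures the primary endpoint; Section 7 and Aim 1.1 do not support that, so the lock must be paired with reporting of the CI-to-DOT change.

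Other parts of the objection also stand:

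- **Live viewing is an inference.** The radiologist may only supervise a technologist. The duty to confirm the lesion's location makes viewing likely, but the text does not state it for every case.
- **The other readers are not shown to be barred from the new images.** The exclusion covers the biopsy exam, which is separate from the DOT acquisition before it. The text does not say whether readers 2 and 3 see the co-registered ultrasound. If they do, the contrast narrows to live versus stored images.
- **Figures 3 and 4 are not shown** and might give the order of the forms.
- **The 33% and 57% figures need the first reader to decide success alone.** Nothing in the documents says so. The illustration also ignores second-look upgrades.

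What does not stand is that the point therefore falls away. The recorded DOT impact and the CI-alone versus CI-plus-DOT comparison are planned outputs, and both are affected if the first reader's CI form precedes the scan.

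**Conclusion.** The point holds in a limited form. On the visible text, the first reader's CI form may precede or follow the repeat ultrasound. If it precedes, that reader's recorded DOT impact and contribution to the sensitivity comparison can mix a second-look effect with the optical effect. Separately, the primary specificity counts a second-look downgrade as DOT benefit in either order.

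The size is unknown. With true specificity at 30% and an assumed 5 to 7 added points, the false-success chance goes from 2.2% to about 7% to 10% under three-reader averaging. The 33% to 57% range is the extreme in which the first reader alone decides, and should not be read as the expected inflation. The added points are assumptions, and the averaged figures use a one-binomial approximation.

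The documents do not support saying that the plan directs the CI form to be completed before the scan, that all 300 first-reader reads are affected, or that the specificity estimate is known to be biased. The change is worth making because it is cheap and the timing cannot be reconstructed afterwards.

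**What to change.** 1. In Sections 5 and 7, require the first reader to complete, time-stamp and lock the CI form after the co-registered ultrasound acquisition and before any reconstructed optical data are released.
2. In Section 10.4, alongside the primary result, report specificity and sensitivity on the CI form and on the DOT form, with the CI-to-DOT change. Attribute only that change to the optical data.
3. Show these results for the first reader separately from readers 2 and 3.

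Cost: one sentence on timing, a time stamp on an existing form, and added tables from data already collected. Reconstruction already follows the visit, so the workflow barely changes, and the sample size is unaffected.

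Downside: the first reader's CI read will include the repeat ultrasound and so differ from the other readers' CI read, which rests on pre-existing data. The lock does not remove that difference; the separate table makes it visible.
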